8.3.6 SERIOUS ADVERSE EVENT REPORTING

SAEs associated with intranasal insulin will be reported to the IRB in accordance with the University of Michigan IRBMED reporting guidelines and to the FDA according to the regulations found in 21 CFR 312.32.

8.3.7 REPORTING EVENTS TO PARTICIPANTS

Participants who experience an AE will be told at the time the event is identified.

8.3.8 EVENTS OF SPECIAL INTEREST

Not applicable.

8.3.9 REPORTING OF PREGNANCY

Any participant with a positive pregnancy test will be notified of the test result and withdrawn or excluded from the study.

8.3.10 DEFINITIONS OF SELECTED OR ANTICIPATED ADVERSE EVENTS

The adverse events identified below are anticipated and will be tracked.

Allergic reaction
 Aspiration
 Nasal irritation
 Sneezing
 Warm feeling in nostrils
 Congestion/Rhinitis
 Lightheadedness
 Nausea and vomiting
 Nosebleeds
 Hypoglycemia
 Headache
 Weakness
 Upper respiratory infection
 Rash

8.4 UNANTICIPATED PROBLEMS

8.4.1 DEFINITION OF UNANTICIPATED PROBLEMS (UP)

Any incident, experience or outcome that is unexpected in nature, severity or frequency that is related or possibly related to study participation will be deemed an unanticipated problem. The impetus for actions related to the unanticipated problem will depend on the information that suggests that the research study procedure places participants at greater risk of harm than previously recognized.

8.4.2 UNANTICIPATED PROBLEM REPORTING

Any unexpected AE and unanticipated problem will be reported to the University of Michigan IRBMED according to their reporting guidelines. Upon becoming aware of any incident, experience, or outcome (not related to an adverse event) that may represent an unanticipated problem, the investigator should assess whether the incident, experience, or outcome represents an unanticipated problem. The incident, experience, or outcomes is considered unanticipated if it meets all of the following criteria:

Unexpected (in terms of nature, severity, or frequency);
Related or possibly related to participation in the research; and
Suggests that the research places subjects or others at a greater risk of harm than was previously known or recognized.

Unanticipated problem Reporting: Per 21 CFR 312.66, 312.53 (c)(1)(vii), and 56.108(b)(1), should an Unanticipated problem occur during the investigation, the investigator will promptly report all unanticipated problems involving risks to human subjects or others to the IRB /FDA.

8.4.3 REPORTING UNANTICIPATED PROBLEMS TO PARTICIPANTS

Reporting unanticipated problems to participants will occur as directed by the UM IRBMED.

9 STATISTICAL CONSIDERATIONS

9.1 STATISTICAL HYPOTHESES

- Primary Efficacy Endpoint(s): Severe hypoglycemia (DLT) as defined by blood glucose <45mg/dL.

The maximum dose that is under the threshold of a 0.9 probability of having a DLT proportion of greater than 0.1 will be considered the maximum tolerated dose for this study.

- Secondary Efficacy Endpoint(s): Change in blood glucose, insulin, and C-peptide levels for up to 4 hours after drug administration to evaluate for any systemic absorption of intranasal insulin.

Our main secondary hypothesis is the secondary efficacy endpoints are not associated with increasing doses of insulin. For example, change in blood glucose from baseline to 4 hours will be similar in the placebo and highest doses.

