This phase 1 study will evaluate the safety and tolerability of intranasal regular humulin insulin in healthy volunteers. The establishment of maximum tolerated dose for intranasal insulin in healthy participants will elucidate the doses to explore in future dose-finding OHCA efficacy studies. Understanding the maximum tolerated dose is also important because the proposed community use of the intervention by bystanders and first responders demands a larger margin of safety than typical drugs, as errors in administration and the potential for misdosing may increase in community use. Therefore, the maximum tolerated dose is needed to estimate the safety margin and therapeutic index of the intervention.

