6.1.2 DOSING AND ADMINISTRATION

Rules for assigning patients

Within subject rules (subject progressing through tiers for cohort):

1. If a volunteer experiences severe hypoglycemia (blood glucose <45 mg/dL), they will be assigned a dose 100 U less for the next round and for all subsequent rounds.
2. If a volunteer experiences severe hypoglycemia a second time, they will be withdrawn from the study.

Study wide rules (determine which dose tiers are allowable for all future volunteers):

1. All doses from 0 to 1000 U by increments of 100 U will be eligible for testing in the study.
2. If there is greater than 0.9 probability that a dose has a greater than 0.1 toxicity rate, that dose will be removed for all future cohorts (see below).

Allocation Rules

Initial Allocation and Strategy:

Overall, the philosophy of allocation is to assign as many patients as possible to higher doses, while also limiting exposure to toxic doses. The trial will start the first cohort with 200, 400, 600, 800, and 1000 U.

Allocation Adjustment Rules:

After each hypoglycemic event, we will recalculate the toxicity probabilities for that dose to see if a dose removal threshold has been met.

If a dose meets the criteria for removal, that dose and all higher doses will be removed from future participants and cohorts. For the next cohort or patient within a cohort, the highest additional doses available will be used. For example, if 700 U was removed, then 200, 300, 400, 500, 600 U would be the new future allocation.

If a cohort completes with no observed episodes of dose-limiting toxicity (DLT), the smallest (and any smaller) doses will drop, and the highest unused dose will replace it. For example, after zero episodes of DLT in Cohort 1 at any dose, Cohort 2 will use 400, 600, 800, 900, and 1000 U. Doses 100 and 200 U will be dropped.

If a cohort has any DLT, but no dose is dropped (only 1 DLT in two different doses for example), the initial allocation rules will be used for the next cohort (200, 400, 600, 800, 1000 U).

4 Cohort Example - No DLT (Demonstrated by Schema Figure 1.2.2)

Cohort 1: Participants #1 to 6

The doses will be 0, 200, 400, 600, 800, and 1000 U.

Cohort 2: Participants #7 to 12

If there were 0 events in Cohort 1, then the doses for Cohort 2 will be 0, 400, 600, 800, 900, and 1000 U. 200 U will be dropped and 900 U will be entered.

Cohort 3: Participants #13 to 18

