7 STUDY INTERVENTION DISCONTINUATION AND PARTICIPANT DISCONTINUATION/WITHDRAWAL

7.1 DISCONTINUATION OF STUDY INTERVENTION

The rules for stopping or changing an individual dosing regimen are given above in the Dosing and Administration section.

Rules for discontinuing a dose

We are interested in proceeding with a dose if we remain confident that the Dose Limiting Toxicity (blood glucose < 45 mg/dL) is < 0.1 (1 in 10).

Using the Bayesian Toxicity Monitoring software from MD Anderson (<https://ibl.mdanderson.org/BTM/>)

We define Toxicity parameters as:

Probability of DLT is represented by θ

Maximum probability of DLT allowed (θ_{\max}): 0.1

When calculating the probability of DLT at a dose, we will use a Beta(0.2,0.8) prior. This is a vague prior with a median of 0.2 and a 95% credible interval from 0 to 0.94. There is greater density over probabilities of DLT near zero in this non-symmetric distribution. Each DLT is added to the A parameter of the beta distribution, and each patient who is DLT free is added to the B parameter of the B distribution. Therefore, with the prior included, if 24 participants have DLT on a dose, the probability of DLT can be described with a Beta(0.2,24.8) distribution. In this setting, the posterior estimate for DLT probability is 0.008 (or 0.8%). In addition, the probability that that dose has a DLT proportion over 0.1 is only 0.006 (or 0.6%).

$\text{Prob}(\theta > \theta_{\max}) \geq 0.9$ (Or that there is 90% or greater probability that the DLT is greater than 0.1)

We define the probability that $\text{Prob}(\theta > \theta_{\max})$ as the final output of the trial for each dose. For each dose, we will also calculate the probability that toxicity is greater than 0.1 at that dose.

The below table (SB1A) illustrates the probability that DLT is greater than 0.1 based on the number of observed events.

Table SB1A: Probability of Early Stopping
Number of Toxicities
(Highlighted = Prob(e > 0.1) >= 0.9)

	0	1	2	3	4	5	6	7	8	9	10	11	12	13	14	15	16	17	18	19	20	21	22	23	24
Number of Patients																									
6	.0884	.6292	.9196	.9990	.9993	1.0000	1.0000	NA	NA	NA	NA	NA	NA	NA	NA	NA	NA	NA	NA	NA	NA	NA	NA	NA	NA
12	.0333	.3613	.7196	.9151	.9816	.9971	.9997	1.0000	1.0000	1.0000	1.0000	1.0000	1.0000	NA	NA	NA	NA	NA	NA	NA	NA	NA	NA	NA	NA
18	.0141	.2027	.5135	.7773	.9220	.9786	.9954	.9992	.9999	1.0000	1.0000	1.0000	1.0000	1.0000	1.0000	1.0000	1.0000	1.0000	1.0000	1.0000	NA	NA	NA	NA	NA

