9.2 SAMPLE SIZE DETERMINATION

Overall, for any dose we estimated whether the study would end, with different assumptions of the probability of toxicity for a given dose. These ranged from 0.01 to 0.25. It is possible, however, that a dose tier may not be desirable despite having not been dropped. For example, there will be about an 82% probability that the toxicity rate is > 0.1 if 4 out of 24 participants experience a DLT, then the point estimate using the Bayesian model will be that arm has a 0.17 probability of DLT (slightly above the raw observed rate of 0.125 due to the Bayesian prior).

The design has approximately 80% “power” at the margin (scenario 5). That is, if the true rate of DLT is 0.1 at a dose, the DLT will NOT be declared toxic using the pre-specified definition ($\text{Prob}(\theta > 0.1) \geq 0.9$) just under 80% of the time.

It is important to note that the table below is for a single dose with 24 observations. As the trial progresses, we will generate independent estimates of the probabilities for each dose. The average number of patients indicates that the dose will stop early some proportion of the time. The average number of toxicities provides the average number of DLTs observed within a simulated trial when the true probability of toxicity is given (for example 0.1 in scenario 5).

Table: Operating Characteristics for a Dose Assuming N of 24

Scenario	Prob.Of.Tox	Prob Early.Stop	ProbDeclare.Tox	Avg.N.Patients	Avg.N.Tox	Obs.Tox.Rate
1	0.01	0.0016	0.0016	23.9724	0.2397	0.0104
2	0.025	0.0105	0.0105	23.8235	0.5956	0.0272
3	0.05	0.0453	0.0467	23.2792	1.164	0.0583
4	0.075	0.1062	0.1125	22.3836	1.6788	0.0921
5	0.1	0.1898	0.2062	21.1965	2.1196	0.127
6	0.125	0.2892	0.3196	19.8036	2.4754	0.1617
7	0.15	0.3962	0.4415	18.2978	2.7447	0.1952
8	0.2	0.6031	0.669	15.277	3.0554	0.2563
9	0.25	0.7684	0.8336	12.6203	3.1551	0.3089

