9.4 STATISTICAL ANALYSES

9.4.1 GENERAL APPROACH

For each dose DLT probability θ , we will calculate the $\text{Prob}(\theta > 0.1)$. The maximum dose that is under the threshold of a 0.9 probability of having a DLT proportion of greater than 0.1 will be considered the maximum tolerated dose for this study.

We will also report the observed toxicity rate for each dose. Depending on the number of DLT observed, we may fit a dose response model that uses data from all doses to fit a dose-toxicity curve. We also will plan to use dose response models for the analyses of the secondary endpoints.

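### The MTD is defined by the 0.9 dose-removal cut-off alone, so it means the highest dose not yet shown toxic, with no minimum exposure and no separate test of tolerability

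*Combined protocol and SAP*

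**What the plan says.** Section 6.1.2 sets the study-wide removal rule, which applies to every later cohort: "If there is greater than 0.9 probability that a dose has a greater than 0.1 toxicity rate, that dose will be removed". Section 7.1 sets the limit of 0.1 ("Maximum probability of DLT allowed"), the same 0.9 cut-off and the prior: "When calculating the probability of DLT at a dose, we will use a Beta(0.2,0.8) prior". Section 9.2 adds that each dose gets its own independent estimate.

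Section 9.1 then defines the MTD with the same number: "The maximum dose that is under the threshold of a 0.9 probability of having a DLT proportion of greater than 0.1 will be considered" the MTD. Section 9.4.1 repeats the rule: that dose "will be considered the maximum tolerated dose for this study". Neither section asks for a minimum number treated at the dose, a limit on its estimated DLT rate, or evidence that the rate is below 0.1.

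Two other statements bear on this. Section 7.1 opens its rules with "We are interested in proceeding with a dose if we remain confident that the Dose Limiting Toxicity" is below 0.1. Section 9.2, introducing the case of 4 DLTs in 24 participants, says: "It is possible, however, that a dose tier may not be desirable despite having not been dropped".

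**The concern.** A removal rule and a declaration rule answer different questions. A demanding threshold for removal stops a dose being abandoned on one or two chance events. Used alone to declare the MTD, the same threshold reverses the burden of proof: a dose counts as tolerated until there is 90% probability that it is not. Weak evidence, or none, then works in the dose's favour.

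Determining the MTD is the only primary objective (section 3). Sections 2.1 and 4.3 say it will be used to estimate the safety margin and therapeutic index for use by bystanders and first responders, a setting that "demands a larger margin of safety than typical drugs". A reader who takes the declared MTD as a dose shown to be tolerated would be reading more into it than the rule provides.

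**Working it through.** **Inputs.** Prior Beta(0.2, 0.8), limit 0.1 and cut-off 0.9 (section 7.1); looks at 6, 12, 18 and 24 participants with removal at 2, 3, 4 and 5 DLTs (Table SB1A and the text after it); default schedule 200, 400, 600, 800, 1000 U after a cohort with a DLT but no dropped dose (section 6.1.2).

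**Formula.** With x DLTs in n participants, the posterior is Beta(0.2 + x, 0.8 + n − x), and the quantity used is P = Prob(θ > 0.1) under it.

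**Reproducing the plan.** The boundaries give 2/6 = 0.9196, 3/12 = 0.9151, 4/18 = 0.9220 and 5/24 = 0.9310, all as printed. An exact binomial recursion with these looks and boundaries reproduces the early-stopping, declared-toxic and mean-sample-size columns of the section 9.2 table for all nine scenarios; at a true rate of 0.10 it gives early stop 0.1898, declared toxic 0.2062 and mean N 21.1965.

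**A dose with 4/24 DLTs.** The posterior is Beta(4.2, 20.8), with mean 4.2/25 = 0.168, 95% credible interval 0.052 to 0.334, and P = 0.819. This is below 0.9, so the dose is kept and can be the MTD. (Section 9.2 gives the raw rate as 0.125, which is 3/24; 4/24 is 0.167. This does not affect the point.) With other sample sizes a kept dose can sit higher still: 2/7 = 0.891, 3/13 = 0.896, 4/20 = 0.892.

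**How often a dose above the limit escapes.** One minus the declared-toxic column in section 9.2:

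| True DLT rate | Declared toxic | Not declared toxic |
|---|---|---|
| 0.15 | 0.4415 | 0.5585 (56%) |
| 0.20 | 0.6690 | 0.3310 (33%) |
| 0.25 | 0.8336 | 0.1664 (17%) |

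**A dose with no data.** With n = 0 the posterior is the prior, and P = 0.408, below 0.9, so the dose passes. The plan's rules allow this to matter:

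- Suppose 1000 U is given to all 24 participants and the DLTs fall on participants 6, 12, 18, 23 and 24.
- Each cohort has a DLT, so the default schedule stays in force and 900 U is not scheduled.
- 1000 U is the last administration, so the within-subject step-down never produces a 900 U exposure.
- The running values are 1/6 = 0.629, 2/12 = 0.720, 3/18 = 0.777 and 4/23 = 0.839 (all kept), then 5/24 = 0.931 (removed).
- 900 U, given to nobody, is then the highest dose under the threshold.

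**How often that happens.** The documents give no dose-toxicity curve, so one has to be assumed. Take DLT rates of 1, 1, 2, 3, 4, 6, 8, 12, 18 and 25% at 100 to 1000 U, independent DLTs, and removal checked after each event with reallocation within the cohort (sections 6.1.2 and 9.4.6). Simulation with 4,000 runs per setting puts an MTD that nobody received at about 1% or less. With a milder curve reaching 6% at 1000 U it is 0.1% or less.

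**The case against.** The best defence is that the plan discloses most of this. Section 9.2 presents the 4/24 case itself and separates not dropped from desirable, and its table contains the escape rates as complements. Section 7.1 makes Prob(θ > 0.1) the final output for each dose, and section 9.4.1 adds observed rates and a possible dose-toxicity curve. A dose with 4/24 DLTs would be reported with its 0.82 beside it. All of that stands, and it rules out saying that the plan hides the problem or that the MTD is its only output. It does not change which dose is named: the caveat in 9.2 is not carried into 9.1 or 9.4.1, and the curve is optional.

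A second defence is that the section 7.1 sentence about remaining confident concerns proceeding with a dose, not declaring an MTD. That is fair. It shows the intent, but it does not formally contradict the definition.

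Third, if no DLTs occur the top doses are all tested and the issue does not arise. This is true, but the definition only does work when DLTs occur.

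A reader might also infer that the rule will often name an untested dose. Checking removal only at the end of each cohort gives 5 to 6% under the steep curve. The documents do not support that reading: section 6.1.2 requires recalculation after each hypoglycemic event, and sections 6.1.2 and 9.4.6 change doses within the cohort.

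**Conclusion.** The concern holds as a defect in the definition. Followed exactly, sections 9.1 and 9.4.1 can name as MTD a dose that the plan's own model considers 82% likely to exceed the limit, or a dose with no data. The first is the more important. Its size comes from the plan's own table and needs no assumption beyond those behind that table: escape rates of 56%, 33% and 17% at true DLT rates of 0.15, 0.20 and 0.25, for a single dose planned for 24 participants. The untested-dose case is a real gap but a rare path, about 1% or less under an assumed steep curve.

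A reader might go further and conclude that most trials run this way would declare a dose whose true DLT rate exceeds 0.1. The documents do not support a figure for that. Under the steep curve the proportion runs from about 47% to 67%, depending on how the removal rule is read, and it is driven by setting the top three doses at 12, 18 and 25%. Under the milder curve no dose exceeds 0.1, so the proportion is zero.

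One ambiguity should be settled at the same time. The definition does not say that removed doses are excluded, so a dose removed only because a lower one was dropped could have its own P below 0.9.

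**What to change.** Leave the 0.9 cut-off in sections 6.1.2 and 7.1 as the in-trial removal rule. In sections 9.1 and 9.4.1, define the MTD as the highest non-removed dose that:

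1. was actually given to a pre-stated minimum number of participants, for example one cohort of 6; and
2. has Prob(θ > 0.1) below a separate, pre-stated declaration cut lower than 0.9, for example 0.5, with the value chosen and justified by the sponsor.

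Both parts are needed, because an untested dose (0.408) would pass a 0.5 cut on its own. At 0.5, the most DLTs allowed would be 0/6, 1/12, 1/18 or 2/24, against 1/6, 2/12, 3/18 or 4/24 now. State that the MTD is reported as not established if no dose qualifies, and report the MTD with its n, DLT count and Prob(θ > 0.1).

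Do not add a requirement that every lower tested dose also meet the cut. One DLT in six at a low tier (0.629) would then cap clean higher doses.

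The cost is wording in two sections, with no change to dosing, allocation or sample size. The downside is that the declared MTD will sometimes be lower, possibly by more than one tier: on the default schedule the tested doses are 200 U apart, so moving down one tested dose is already two 100 U tiers.

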Approach: The maximum tolerated dose between 100 – 1000 U of regular short-acting insulin will be determined with an adaptive dose-escalation phase I safety study performed in 24 healthy volunteers. The primary safety outcome will be severe hypoglycemia using a numerical cutpoint of serum glucose <45 mg/dL. Secondary endpoints will include the change in blood glucose, serum insulin, and serum C-peptide levels for up to 4 hours after drug administration to evaluate for any systemic absorption of intranasal insulin.

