4.3 JUSTIFICATION FOR DOSE

There is substantial clinical safety data for intranasal insulin in human subjects, but there is no data suggesting the maximum tolerated dose. The majority of existing safety data involve doses of intranasal regular insulin in daily repeated administrations from 20 to 160 U. As reviewed recently by Schmid et al, there were no episodes of hypoglycemia in 1,053 subjects in 38 studies in this dose range (17). Although these data are reassuring, there are at least two important reasons to explore higher dose ranges.

The first reason is to understand the upper limits of the dose that might be explored in future dose-finding efficacy studies. Planned animal studies will refine the dose efficacy response in models of OHCA, but existing data demonstrate efficacy and safety in other animal models in doses that scale to human doses ranging from 300 U to 1000 U (depending on the method of scaling and parameters chosen). It is important to determine if the maximum tolerated dose in humans is within or above these doses.

Understanding the maximum tolerated dose is also important because the proposed community use of the intervention by bystanders and first responders demands a larger margin of safety than typical drugs, as errors in administration and the potential for inaccurate dosing may increase in community use. A maximum tolerated dose is needed to estimate the safety margin and therapeutic index of the intervention. The therapeutic dose will be estimated from ongoing animal experiments.

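### The MTD rule has no outcome for an MTD that was not reached, so whenever 1000 U is retained, even with no DLTs, the top of the tested range is declared the MTD

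*Combined protocol and SAP*

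**What the plan says.** The MTD is defined in Section 9.1, and again in 9.4.1, as "The maximum dose that is under the threshold of a 0.9 probability of having a DLT proportion of greater than 0.1"; that dose "will be considered the maximum tolerated dose for this study". The dose grid is fixed in 6.1.2: "All doses from 0 to 1000 U by increments of 100 U will be eligible for testing in the study". When no DLTs occur, 6.1.2 moves the allocation to the five highest doses (600 to 1000 U) and keeps it there. Nothing in these sections says what to conclude if no dose meets the removal criterion.

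Section 4.3 gives the purpose. Animal data show efficacy and safety "in doses that scale to human doses ranging from 300 U to 1000 U", and the protocol continues: "It is important to determine if the maximum tolerated dose in humans is within or above these doses". It adds: "A maximum tolerated dose is needed to estimate the safety margin and therapeutic index of the intervention".

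The stated scope varies. Section 4.1 limits it: "The maximum tolerated dose between 100 – 1000 U of regular short-acting insulin will be determined". The primary objective in the synopsis (1.1) and in Section 3 is to determine the MTD in healthy participants, with no range attached.

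**The concern.** A trial that finds no limiting dose has a right-censored answer: the MTD is at least the highest dose tested. The rule in 9.1 has no place for that answer. It gives the label MTD to the highest dose not removed, whether the next step up would have been toxic or nothing higher could be tried. If 1000 U is retained, the declared primary conclusion has the form of an estimate, although a DLT-free top dose gives only a lower bound.

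This matters because 4.3 asks whether the MTD falls inside the scaled range or beyond it, and because 2.1 and 4.3 intend to use the MTD for a safety margin and therapeutic index. A margin built on a censored value is itself only a lower bound. The label also does not separate a clean result at 1000 U from one just short of removal.

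**Working it through.** **Inputs.** Prior: "When calculating the probability of DLT at a dose, we will use a Beta(0.2,0.8) prior" (7.1). Maximum DLT rate 0.1 and removal when Prob(θ > 0.1) ≥ 0.9 (7.1). Looks after 6, 12, 18 and 24 participants (Table SB1A). Grid 0 to 1000 U (6.1.2).

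**1. Reproduce the plan's figures.** With x DLTs in n participants the posterior is Beta(0.2 + x, 0.8 + n − x). The smallest x with Prob(θ > 0.1) ≥ 0.9 is 2 of 6, 3 of 12, 4 of 18 and 5 of 24, as in 7.1. Carrying these thresholds through an exact sequential binomial calculation reproduces the nine rows of the 9.2 table. For scenario 5 (true rate 0.1) the early-stop probability is 0.1898, the probability of being declared toxic is 0.2062 and the mean N is 21.1965. The dose is therefore kept with probability 1 − 0.2062 = 0.7938, the plan's figure of just under 80%.

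**2. How often 1000 U is kept, as a single dose with 24 observations.** This is 1 − ProbDeclare.Tox:

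| True DLT rate at 1000 U | Declared toxic | Kept |
|---|---|---|
| 0.01 | 0.0016 | 0.9984 |
| 0.025 | 0.0105 | 0.9895 |
| 0.05 | 0.0467 | 0.9533 |
| 0.10 | 0.2062 | 0.7938 |

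With zero DLTs it is kept with certainty.

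**3. How often 1000 U is the declared MTD in the whole trial.** Removing a lower dose also removes every higher dose (6.1.2), so 1000 U can be lost without any DLT at 1000 U, and step 2 overstates how often it survives. The allocation scheme was simulated (at least 4,000 runs per curve) under these assumptions: DLTs independent across administrations, removal thresholds applied at the number exposed rounded up to a multiple of 6, and the dose–DLT curves below, which are illustrative and not from the protocol.

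| Assumed DLT rate | 1000 U is the declared MTD |
|---|---|
| none at any dose | 100% |
| 0.01 at every dose | about 99% |
| 0.025 at every dose | about 94% |
| 0.05 at every dose | about 76% |
| rising linearly to 0.05 at 1000 U | about 88% |

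**4. What the label covers.** In the protocol's no-DLT example (6.1.2), 1000 U is in all four cohorts, so 4 × 6 = 24 are exposed. Any count from 0 to 4 DLTs in 24 keeps 1000 U:

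| DLTs in 24 | Prob(θ > 0.1) | Declared MTD |
|---|---|---|
| 0 | 0.006 | 1000 U |
| 1 | 0.112 | 1000 U |
| 2 | 0.346 | 1000 U |
| 3 | 0.615 | 1000 U |
| 4 | 0.819 | 1000 U |

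At 0/24 the posterior mean is 0.2/25 = 0.008 and the exact 95% interval is 0 to 14.2%. At 4/24 they are 4.2/25 = 0.168 and 4.7% to 37.4%. The first supports an MTD of at least 1000 U. The second is short of removal but gives little assurance that the DLT rate is below 0.1.

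**The case against.** The strongest reply is that the plan already limits and qualifies its result. Section 4.1 puts the search between 100 and 1000 U, and 9.1 and 9.4.1 confine the MTD to this study. The ceiling follows from the product and volume in 6.1 (500 U/mL × 2 mL = 1000 U). Section 7.1 makes Prob(θ > 0.1) the final output for each dose and works through a Beta(0.2, 24.8) posterior, giving 0.008 and 0.006. Section 9.4.1 adds observed rates per dose, 9.4.2 adds 95% intervals, and 9.2 warns that a dose may be undesirable although it was not dropped.

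Much of this stands. A reader might infer that the trial cannot answer the question in 4.3 at all. The documents do not support that: 0/24 with a probability of 0.006 lets a careful reader conclude that the MTD is at least 1000 U, though not how far above. A reader might also infer that the rule always returns a dose. It may not: if 500 U is dropped, 7.1 sends the study to an amended plan or discontinuation.

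What the reply does not do is correct the declared result. Neither the scope statement nor the words confining the MTD to this study says what to report when no limit is found, and the objective in 1.1 and Section 3 carries no range.

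**Conclusion.** The point holds as a fault in the stated conclusion rule. The declared MTD can never exceed 1000 U, and a retained 1000 U is labelled the MTD even when a DLT-free result supports only a lower bound. How often this happens depends on the true DLT rates. It is certain with no DLTs. Under the assumed curves with rates up to 0.05, it occurs in about 76% to 100% of trials, given independent DLTs and the threshold rounding described above.

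Three stronger readings go too far:

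- **That the protocol expects few or no DLTs.** It gives no expected DLT rate at 200 to 1000 U. The zero-hypoglycemia record in 1,053 subjects covers 20 to 160 U, 2.3.3 says the shape of the dose response is not established, and 9.2 examines rates from 0.01 to 0.25. The no-DLT case is one the protocol works through, not one it predicts.
- **That 1000 U would be declared in roughly 95% or more of trials at rates up to 0.05.** That is the single-dose figure; whole-trial figures can be lower.
- **That the reported margin is capped at 1000/1000 = 1.0 to 1000/300 = 3.3-fold.** This treats 300 to 1000 U as the therapeutic dose, which 4.3 says is still to be estimated. Section 9 plans no margin calculation.

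**What to change.** In 9.1 and 9.4.1, add an outcome for the case where 1000 U has not been removed at the end of the study: *no dose met the removal criterion; MTD not reached within the range tested (highest dose 1000 U)*. Always report with it the DLT count, the number exposed, Prob(θ > 0.1) and an interval for the DLT rate at 1000 U, so that 0/24 and 4/24 can be told apart.

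State that any later safety margin or therapeutic index based on that result is a lower bound, to be read with the same figures. Align the objective in 1.1 and Section 3 with the 100 to 1000 U scope already in 4.1.

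The cost is wording, best settled before results are seen. Dosing, sample size and analysis do not change. The downside is a less definite headline result when 1000 U is retained.
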